1 SAP SYNOPSIS

TITLE OF STUDY: A Phase 3 Randomized, Double-Blind, Placebo-Controlled, Multicenter Study to Evaluate the Efficacy and Safety of BMN 111 in Children with Achondroplasia
PROTOCOL NUMBER: 111-301
STUDY SITES: Approximately 33 clinical centers worldwide
PHASE OF DEVELOPMENT: Phase 3

OBJECTIVES:
 
The primary objective of the study is to:
 
 • Evaluate change from baseline in annualized growth velocity at 52 weeks in subjects treated with BMN 111 compared with control subjects in the placebo group 
The secondary objectives of the study are to:
 
 • Evaluate change from baseline in height Z-score in subjects treated with BMN 111 compared with control subjects in the placebo group at 52 weeks • Evaluate change from baseline in upper:lower body segment ratio in subjects treated with BMN 111 compared with control subjects in the placebo group at 52 weeks • Evaluate change from baseline in body proportion ratios of the extremities • Evaluate effect of BMN 111 on bone morphology/quality by X-ray and dual X-ray absorptiometry (DXA) • Evaluate potential changes in health-related quality of life (HRQoL) as measured by the Quality of Life in Short Stature Youth (QoLISSY) and the Pediatric Quality of Life Inventory (PedsQL) questionnaires • Evaluate potential changes in functional independence as measured by the Functional Independence Measure (Wee-FIM) clinician-reported outcome • Evaluate safety and tolerability of BMN 111 in children with ACH • Evaluate the pharmacokinetics of BMN 111 • Evaluate immunogenicity of BMN 111 and assess impact on safety, PK, and efficacy measures • Evaluate change from baseline in bone metabolism biomarkers 
The exploratory objectives of the study are to:
 
 • Evaluate sleep study scores by polysomnography in a subset of subjects • Evaluate biomarkers of BMN 111 activity • Evaluate genomic biomarkers

Study 111-301 Statistical Analysis Plan

STUDY DESIGN AND PLAN: This is a phase 3 randomized, double-blind, placebo-controlled, multicenter study to evaluate the effect of BMN 111 on growth velocity in children with ACH. Subjects who are 5 to < 18 years old, with documented ACH confirmed by genetic testing who have been enrolled in Study 111-901 for at least a 6-month period immediately before study entry, and meet all study eligibility criteria, will participate. Approximately 33 clinical centers worldwide will participate in the study.

At least 110 eligible subjects will be stratified based on sex and Tanner stage (Stage I, and > Stage I, with no more than 20% of subjects > Tanner Stage I) at Screening, and randomly assigned in a 1:1 ratio to one of two treatment groups (placebo or BMN 111 at 15µg/kg).

After subjects have completed the treatment period of the study, those in both treatment and control groups may be eligible to receive BMN 111 in the extension study 111-302 after the Week 52/Study Completion Visit.

ANALYSIS POPULATIONS:

The Full Analysis Set (FAS) includes all randomized subjects with a signed informed consent. The FAS will be used for all efficacy analyses. When applicable, additional sensitivity analyses will be carried out for the Per-Protocol (PP) population, defined as a subset of the FAS who are compliant with the protocol and do not have major protocol violations that affect the interpretability of efficacy data.

The Safety Population is a subset of the FAS, and defined as all randomized consented subjects who receive at least one dose of double-blinded BMN 111 or placebo in this study.

The PK Population is defined as all subjects in the FAS randomized to the BMN 111 treatment group, who receive at least one dose of BMN 111 in this study and have at least one evaluable PK concentration.

The Immunogenicity Population is defined as all subjects in the Safety Population who have at least one evaluable immunogenicity sample.

STUDY ENDPOINTS AND ANALYSES:

Primary efficacy endpoint:

The primary efficacy endpoint is the change from baseline in annualized growth velocity (AGV, cm/yr) at week 52.

The primary analysis of the change from baseline in AGV at week 52 will be performed using an ANCOVA model. Missing values will be imputed, either using multiple imputation (MI) techniques or (if there is insufficient data to perform MI) alternative approaches to address missing data. Details of missing data imputation can be found in Section 14.3.2.

The following sensitivity analysis and supplementary analyses will be performed to assess the robustness of the results of the primary analysis.

- Primary analysis using the washout model (sensitivity).
- Primary analysis on completers (supplementary).
- Primary analysis excluding assessments that occur post limb lengthening or receipt of growth hormone/gonadotropin-releasing hormone (supplementary).

Key secondary efficacy endpoints:

These key secondary efficacy endpoints will be tested using hierarchical testing which controls the type I error rate (otherwise referred to as confirmatory testing):

Study 111-301 Statistical Analysis Plan

- Change from baseline in height Z-score at week 52
- Change from baseline in upper to lower body segment ratio at week 52

Other secondary efficacy endpoints:

Non-confirmatory statistical testing will be performed for the secondary endpoints identified below (*). Other endpoints will be summarized using descriptive statistics only.

- Change from baseline in upper arm length to lower arm ratio*
- Change from baseline in upper leg length to knee to heel ratio*
- Change from baseline in upper leg length to tibial length ratio*
- Change from baseline in arm span to standing height ratio*
- Change from baseline in growth measures* (see Section 14.5.2 for list of measures)
- Change from baseline in body mass index
- Change from baseline in body mass index Z-score
- Change from baseline in weight Z-scores
- Change from baseline in pediatric quality of life inventory (PedsQL)
- Change from baseline in quality of life short statured youth (QoLISSY)
- Change from baseline in functional independence measure (Wee-FIM).

Safety endpoints and analyses:

Adverse events (AEs) will be coded using Medical Dictionary for Regulatory Activities (MedDRA) Version 22 and presented by System Organ Class (SOC) and Preferred Term (PT). Summaries of AE's will include all AE's, serious adverse events (SAEs) and events of interest (EOI). Exposure-adjusted summaries will also be provided.

Clinical laboratory tests will be summarized descriptively. Shift tables tabulating Common Terminology Criteria for Adverse Events (CTCAE) severity grade at baseline versus worst post-baseline grade will be provided.

3 LIST OF ABBREVIATIONS

Abbreviation	Definition
µg/kg	microgram/kilogram
ACH	achondroplasia
ADA	anti-drug antibody
ADaM	Analysis Data Model
AE	adverse event
AGV	annualized growth velocity
ANCOVA	analysis of covariance
ANP	atrial natriuretic peptide
ATC	Anatomical Therapeutic Chemical
BMC	bone mineral content
BMD	bone mineral density
BMI	body mass index
BMN	BioMarin
BNP	brain natriuretic peptide
BPV	BioMarin Pharmacovigilance
BSAP	bone-specific alkaline phosphatase
CBCL	Child Behavior Checklist
CRF	case report form
cGMP	cyclic guanosine monophosphate
CNP	c-type natriuretic peptide
CNP22	c-type natriuretic peptide (22 amino acids in length)
CSR	clinical study report
CTCAE	Common Terminology Criteria for Adverse Events (v4.0)
DMC	data monitoring committee
DXA	dual x-ray absorptiometry
ECG	electrocardiogram
ECHO	echocardiogram
eCRF	electronic case report form
FAS	full analysis set
FDA	Food and Drug Administration
GCP	Good Clinical Practice
ICH	International Conference on Harmonisation
ISR	injection site reaction
IXRS	interactive web or voice response system
LOCF	last observation carried forward
LS	least squares
MAR	missing at random
MCAR	missing completely at random
MCP	multiple comparisons procedure
MedDRA	Medical Dictionary for Regulatory Activities
MI	multiple imputation
MMRM	mixed model for repeated measures
NAb	neutralizing antibody
NCI	National Cancer Institute
NMAR	not missing at random
PD	pharmacodynamic

	Study 111-301 Statistical Analysis Plan
---	--

PedsQL	Pediatric Quality of Life Inventory
PK	pharmacokinetic
PP	per-protocol
PT	preferred term
QoLISSY	Quality of Life in Short Statured Youth
QTc-B	Bazett's corrected QT interval
QTc-F	Fridericia's corrected QT interval
SAE	serious adverse event
SAP	statistical analysis plan
SC	subcutaneous
SD	standard deviation
SDTM	Study Data Tabulation Model
SE	standard error
SMQ	Standardized MedDRA query
SOC	system organ class
TAb	total antibody
TEAE	treatment-emergent adverse event
TESAE	treatment-emergent serious adverse event
TLGs	tables, listings, and graphs
WeeFIM	Functional independence measure for children
WHO	World Health Organization

**Study 111-301 Statistical Analysis Plan****4 INTRODUCTION**

Study 111-301 (original protocol effective date: 01-September-2016, Japanese-specific protocol effective date: 18-April-2018) is a Phase 3 randomized, double-blind, placebo-controlled, multicenter study to evaluate the effect of BMN 111 on growth velocity in children with achondroplasia (ACH).

This Final SAP is an amendment to the Final Draft SAP (dated: 15-May-2019). The SAP has been amended to include modifications to address the FDA written response letter dated 25-July-2019. The key updates are summarized in Section 22.

This SAP is based on Amendment 4 of the protocol (date: 01-February-2019), and describes the analyses and evaluations that will be provided for study 111-301, including the data from study 111-901 data for subjects who subsequently enrolled in study 111-301. Where there are major differences between the protocol-defined analyses, and the SAP-defined analyses, these will be identified in the SAP. The SAP-defined analyses prevail.

4.1 Objectives of Study

The primary objective of the study is to:

- Evaluate change from baseline in annualized growth velocity at 52 weeks in subjects treated with BMN 111 compared with control subjects in the placebo group

The secondary objectives of the study are to:

- Evaluate change from baseline in height Z-score in subjects treated with BMN 111 compared with control subjects in the placebo group at 52 weeks.
- Evaluate change from baseline in upper:lower segment body ratio in subjects treated with BMN 111 compared with control subjects in the placebo group at 52 weeks
- Evaluate change from baseline in body proportion ratios of the extremities
- Evaluate effect of BMN 111 on bone morphology/quality by X-ray and DXA
- Evaluate potential changes in health-related quality of life (HRQoL) as measured by QoLISSY and PedsQL questionnaires.
- Evaluate potential changes in functional independence as measured by the WeeFIM clinical-reported outcome.
- Evaluate safety and tolerability of BMN 111 in children with ACH
- Evaluate the pharmacokinetics of BMN 111
- Evaluate immunogenicity of BMN 111 and assess impact on safety, PK and efficacy measures

**Study 111-301 Statistical Analysis Plan**

- Evaluate change from baseline in bone metabolism biomarkers

The exploratory objectives of the study are to:

- Evaluate sleep study scores by polysomnography in a subset of subjects
- Evaluate biomarkers of BMN 111 activity
- Evaluate genomic biomarkers

4.2 Study Design

Study 111-301 is a Phase 3 randomized, placebo-controlled, double-blind multicenter study to evaluate the effect of BMN 111 on growth in children with ACH. Subjects who are 5 to < 18 years old with documented ACH confirmed by genetic testing will have been enrolled in Study 111-901 (observational run-in study in pediatric patients with ACH) for at least a 6-month period immediately before study entry, and meet all study eligibility criteria.

Subjects who discontinue from the study drug will be encouraged to remain in the study and continue to undergo as many of the protocol-specified procedures and assessments as possible for the remainder of the study, as long as such continued participation does not detrimentally affect the health, safety, or welfare of the subject.

[figure not shown]
This 60-week study (up to 4 weeks of screening, 52 weeks of treatment with an additional 4 weeks of safety follow up) allows for assessment of the effect of daily BMN 111 administration on change from baseline in AGV, height, and body proportions in subjects treated with BMN 111 compared with control subjects in the placebo group. In addition, this study will help to further characterize safety and tolerability of BMN 111 in children with ACH.

At least 110 eligible subjects will be stratified based on sex and Tanner stage (Stage I, and > Stage I, with no more than 20% of subjects > Tanner Stage I) at Screening, and randomly assigned in a 1:1 ratio to one of two treatment groups: placebo or BMN 111 at 15 µg/kg. Approximately 33 clinical centers worldwide will participate in the study.

The 111-301 study design is presented below.

	Study 111-301 Statistical Analysis Plan
---	--

Figure 4.2.1: Study Design

Subjects who complete the 52 week treatment period in 111-301 study on randomized treatment, will be eligible to receive open label BMN 111 15 µg/kg daily in 111-302, to assess safety and efficacy of BMN 111 over the longer term. Subjects will have the option to enroll in 111-302 after the Week 52/Study Completion Visit. Week 52 assessments will serve as Baseline assessments for entry to study 111-302 if the visit occurs on the same day or within 2 weeks. Subjects who enroll into 111-302 more than 2 weeks after the 111-301 Week 52 visit will have a separate Baseline visit; the same assessments as those performed at Week 52 will be repeated at that time.

4.3 Study Population

Subjects who are 5 to < 18 years old with documented ACH confirmed by genetic testing, and have been enrolled in Study 111-901 for at least a 6-month period immediately before study entry, and meet all study eligibility criteria will participate in the study.

4.4 Study Dosage and Administration

BMN 111 will be administered as a single subcutaneous dose of 15 µg/kg given daily for 52 weeks. The control group will receive subcutaneous injections with placebo daily for 52 weeks.

4.5 Sample Size Determination

With 55 subjects planned in each of the two randomized groups (one BMN 111 dose group and one placebo group), the power to detect a difference of 1.75 cm/year between the BMN 111 group and the placebo group in change from baseline in AGV at 12 months is

**Study 111-301 Statistical Analysis Plan**

approximately 90%, assuming that the pooled standard deviation of the change from baseline in AGV is 2.80, using a two-sided two-sample t-test at a 0.05 significance level. The power calculation is based on data from Study 111-202 (a phase 2, open-label, sequential cohort dose-escalation study) and Study 111-901.

4.6 Blinding and Randomization Methods**4.6.1 Blinding Method**

This is a placebo-controlled, double-blind study. Blinding is strictly maintained during the study and a study specific masking plan describes how potentially unblinding data (i.e. PK and Biomarker data) are handled during the lifetime of the study. The study will remain blinded until after all data has been entered, and the final database has been locked.

4.6.2 Randomization Method

The centralized randomization with stratification is managed by an external vendor, using IXRS technology. Eligible subjects will be randomized whilst at the site, and receive their first dose of study drug on the same day.

In the original protocol, subjects were stratified based on sex and age (≤ 11 , > 11 years). At the time of protocol amendment 2, the strata were changed and subjects randomized after this time were stratified by sex and Tanner Stage. The original strata will be reported for all subjects; however all statistical analyses will reported as sex and Tanner Stage.

At least 110 eligible subjects will be stratified based on sex and Tanner Stage (Stage I, and $>$ Stage I) (with no greater than 20% of subjects $>$ Tanner Stage I), and randomly assigned in a 1:1 ratio to one of two treatment groups: placebo or BMN 111 at 15 $\mu\text{g}/\text{kg}$.

A separate stratified randomization scheme is in place for PI [REDACTED] subjects. This randomization scheme is set up to assure an overall approximate balance of PI [REDACTED] subjects randomized to both treatment arms. The subjects are stratified based on sex and Tanner Stage (Stage I, and $>$ Stage I), and in addition the blocks across the strata are sequenced to assure an overall balance across the treatment arms.

To achieve sex balance, approximately 50% of each sex will be enrolled, with neither to exceed 55%. For placebo and BMN 111, the route of administration is subcutaneous injection and the frequency is daily. Approximately 33 clinical centers worldwide were expected to participate in the study, with a cap of 11 subjects at each site.

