9.1 Overall Study Design and Plan

This is a Phase 3 randomized, placebo-controlled, double-blind multicenter study to evaluate the effect of BMN 111 on growth in children with ACH. Subjects who are 5 to < 18 years old with documented ACH confirmed by genetic testing will have been enrolled in Study 111-901 for at least a 6-month period immediately before study entry, and meet all study eligibility criteria will participate. At least 110 eligible subjects will be stratified based on sex and Tanner Stage (Stage 1, and > Stage 1) (with no greater than 20% of subjects > Tanner Stage 1), and randomly assigned in a 1:1 ratio to one of two treatment groups: placebo or BMN 111 at 15 µg/kg. To achieve gender balance, approximately 50% of each gender will be enrolled, with neither to exceed 55%. In Japan, subject enrollment will be staggered initially, with a minimum of a 2-week window between the first 4 subjects enrolled.

For placebo and BMN 111, the route of administration is subcutaneous injection and the frequency is daily. Approximately 33 clinical centers worldwide will participate in the study.

The 111-301 study design is presented below in Figure 9.1.1.

Figure 9.1.1: 111-301 Study Design

BMN 111 or placebo will be administered as a single subcutaneous dose of 15 µg/kg given daily for 52 weeks. The control group will receive subcutaneous injections with placebo daily for 52 weeks.

Safety monitoring will be conducted for all subjects randomized to BMN 111 or placebo after the first dose is received and over the duration of the study. This will include a minimum of 2 hours post-dose observation on the first 3 days of dosing and 30 minutes on all

	Study 111-301 Amendment 4	Page 44
---	---------------------------	---------

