22 SUMMARY OF CHANGES TO STUDY SAP

Version		Affected Section (Number of Section in Previous SAP)	Summary of Revisions
Number	Date		
Final SAP	05-Nov-19	1.0 (NA)	Signature page added.
Final SAP	05-Nov-19	4.6.2 (2.6.2)	The Japanese randomization has been described in more detail.
Final SAP	05-Nov-19	5.1.2 (3.1.2)	Gonadotropin-releasing hormones have been added as an exclusion from the Pre Protocol analysis population.
Final SAP	05-Nov-19	5.4 (3.4)	111-901 analysis visit windows have been updated.
Final SAP	05-Nov-19	5.4 (3.4)	A spaghetti plot of standing height Z-scores has been added.
Final SAP	05-Nov-19	8.0 (6.0)	A listing of major deviations classified as “dosing irregularity” has been added.
Final SAP	05-Nov-19	9.0 (7.0)	Baseline characteristics growth measures are re-ordered. Tanner Stages, other than (I,>I) are not included in baseline summary.
Final SAP	05-Nov-19	10.0 (8.0 and Appendix)	Details of Achondroplasia-related terms are removed from the SAP appendix, and located in a study file.
Final SAP	05-Nov-19	10.0 (8.0)	Physical exam results listing added.
Final SAP	05-Nov-19	11.0 (9.0)	The concomitant medications are to be summarized by ATC level 2, not 4.
Final SAP	05-Nov-19	13.0 (11.0)	Definition for missed dose has been added. Dose interruptions have been replaced with a summary of “Reasons for missed dose”.
Final SAP	05-Nov-19	14.0 (12.0)	Estimands have been clarified for the primary and key secondary endpoints. Details have been added to describe imputation methods for missing Week 52 assessments for standing height, AGV, height Z-Score, sitting height and upper-to-lower body segment ratio.
Final SAP	05-Nov-19	14.2 (12.2)	Terminology for the testing strategy has been changed from “statistically significant “ to “confirmatory”.
Final SAP	05-Nov-19	14.3.3 (12.3.3)	There is now one sensitivity analysis and 2 supplementary analyses: A washout model has been introduced as the sensitivity analysis The completers analysis is now a supplementary analysis (not sensitivity). The analysis excluding data post limb lengthening/growth hormone is now a supplementary analysis (not sensitivity). The random coefficient model sensitivity analysis has been removed.
Final SAP	05-Nov-19	14.7 (12.7)	More detail has been added for subgroup analyses, and subgroups of height Z-score thresholds and AGV thresholds have been added
Final SAP	05-Nov-19	15.1.1 (13.1.1)	A table of the incidence of TEAE’s by SOC, PT and highest CTCAE grade has been added.

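### One group is randomised under a separate scheme balanced across arms, but the three confirmatory ANCOVAs have no term for that scheme (optional, low-priority gain in precision)

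*SAP*

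**What the plan says.** SAP 4.6.2 describes the main randomisation, stratified by sex and Tanner stage, and then adds: "A separate stratified randomization scheme is in place for" one group, whose label is redacted. Of its purpose the SAP says: "This randomization scheme is set up to assure an overall approximate balance of" that group between the arms. The scheme uses the same sex and Tanner strata and, beyond that, "the blocks across the strata are sequenced to assure an overall balance across the treatment arms".

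The SAP change log (Section 22), in its entry for 4.6.2, supplies the identity: "The Japanese randomization has been described in more detail". Two other places confirm separate arrangements in Japan. The SAP introduction gives a "Japanese-specific protocol effective date: 18-April-2018", and Protocol 9.1 states: "In Japan, subject enrollment will be staggered initially, with a minimum of a 2-week window between the first 4 subjects enrolled".

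The default covariate list in SAP 14.1 has treatment, a four-level sex-by-Tanner stratum, baseline age, baseline AGV and baseline height Z-score. The model statements in 14.3.2 (AGV) and 14.4.1 (height Z-score) use exactly these. The one in 14.4.2 (upper:lower ratio) adds the baseline ratio. None has a scheme, Japan or region term.

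**The concern.** The SAP models the sex-by-Tanner strata but not the other factor on which it deliberately balanced the arms. If that group still differs in outcome after adjustment for age, baseline AGV, baseline height Z-score and stratum, balancing removes the difference from the true variance of the treatment contrast. The model, however, leaves it in the error term. The reported standard error is then too large, and some power is given away in all three confirmatory tests.

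One sentence in 4.6.2 might seem to settle the matter: "all statistical analyses will reported as sex and Tanner Stage". It closes the account of the Amendment 2 change from age strata to Tanner strata and comes before the separate scheme is introduced. It does not say how that scheme is to be handled.

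**Working it through.** **The plan's own figure.** With 55 per arm, a difference of 1.75 cm/yr, SD 2.80 and two-sided 0.05 (SAP 4.5), the noncentrality is 1.75 / (2.80 × √(2/55)). Power is 0.901 (noncentral t, 108 df) or 0.906 (normal approximation). The stated 90% reproduces.

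**Assumptions, because the documents give no figures.** Group size m runs from 4 (the number whose enrolment Protocol 9.1 staggers in Japan) to 22 (two sites at the limit in 4.6.2, "with a cap of 11 subjects at each site"; the number of sites in Japan is not stated). The gap is the mean difference in change in AGV between this group and the rest after adjustment. I use 0, 1.0 and 2.8 cm/yr; the last is 1.6 times the planned effect (2.8/1.75). The residual SD is 2.80. Group membership is taken as unrelated to the other covariates.

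**Without the term.** The model has 8 parameters, so 110 − 8 = 102 df. With m1 and m0 group members in the two arms:

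- λ = [m1(1 − m1/55) + m0(1 − m0/55)] × gap²/SD²
- the residual sum of squares divided by SD² is noncentral chi-square (102 df, noncentrality λ)
- standard error ratio = √(1 + λ/102)

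Example, 11 v 11 and gap 1.0: λ = 2 × 11 × 0.8 × (1.0/2.80)² = 17.6 × 0.1276 = 2.245. The ratio is √(1 + 2.245/102) = 1.0109.

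**Even split, SD 2.80; power with the term (101 df) is 0.9008 throughout**

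| Group | Gap, cm/yr | SE excess | Type I error | Power without | Points forgone |
|---|---|---|---|---|---|
| any | 0 | 0 | 0.050 | 0.901 | none |
| 4 | 1.0 | 0.24% | 0.0495 | 0.9000 | 0.1 |
| 22 | 1.0 | 1.09% | 0.0476 | 0.8970 | 0.4 |
| 4 | 2.8 | 1.87% | 0.0459 | 0.8942 | 0.7 |
| 22 | 2.8 | 8.28% | 0.0340 | 0.8692 | 3.2 |

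If the covariates explained about half the variance (residual SD 2.0), a gap of 2.8 would give an SE excess of 3.6% (4 subjects) to 15.7% (22) and type I error of 0.042 to 0.024. Power would be 0.994 and 0.989 without the term against 0.995 with it, so under 1 point is forgone.

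**If 2.80 already contains the gap.** The residual variance is then 2.80² − q(1 − q) × gap², with q = m/110. For 22 subjects and gap 2.8 it is 7.84 × (1 − 0.16) = 6.59 (SD 2.57), and power is 0.917 without the term and 0.943 with it. For 4 subjects and gap 1.0 the figures are 0.9013 and 0.9021. The planned 90% holds either way.

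**Uneven split.** The term multiplies the variance of the treatment estimate by 1/(1 − r²), with r² = (m1 − m0)²/[m(110 − m)]. For 3 v 1, r² = 4/(4 × 106) = 0.0094. Without the term the estimate shifts by gap × (m1 − m0)/55, averaged here over both directions. Change in power from adding the term, in points, SD 2.80:

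| Split | Gap 0 | Gap 1.0 | Gap 2.8 |
|---|---|---|---|
| 3 v 1 | −0.28 | −0.14 | +0.79 |
| 4 v 2 | −0.19 | −0.02 | +1.20 |
| 7 v 5 | −0.10 | +0.18 | +2.19 |
| 12 v 10 | −0.06 | +0.37 | +3.52 |

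With an even split and gap 0 the loss is 0.01 points. Type I error without the term never exceeds 0.050.

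**Simulation check.** I simulated the ANCOVA with mirrored blocks in the separate scheme, 10,000 runs per null case. With 4, 8 and 18 group members and a gap of 1 residual SD, type I error was 0.048, 0.044 and 0.040 without the term, and 0.050 to 0.053 with it. The mean treatment estimate was essentially the same in both models.

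**Key secondary endpoints.** The same formula applies in residual SD units. Gaps of 0.25, 0.5 and 1.0 SD make the SE 0.1%, 0.5% and 2% too large with 4 subjects, and 0.5%, 2% and 8% with 22. The ratio model has one fewer degree of freedom, which changes nothing material.

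**The case against.** The strongest reply is that no error is shown. The SAP nowhere promises a term for each randomisation scheme, the separate scheme uses the same sex and Tanner strata that every model contains, and the primary model was fixed after health-authority interaction and blinded data review (14.3.2). Nothing in the documents suggests a residual gap once baseline AGV, height Z-score, age and stratum are in the model. At a moderate gap the gain is under half a power point, and in a small uneven group the term loses power.

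All of that stands, and it is why this is optional. It does not remove the point: the trial balances on a factor, the models omit it, and the SAP does not say that this is intended.

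A reader might go further and infer that the omission biases the treatment effect, inflates type I error or undermines the gatekeeping. The documents do not support this. Allocation is 1:1, the scheme is built to balance the arms, and the error rate is nominal or below in every case examined. Nor can one infer that the planned 90% power is lost: SAP 4.5 gives 2.80 as the pooled SD of the change itself, before covariate adjustment, and on that reading 90% is kept. The redacted label is not a fault in the plan.

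**Conclusion.** The point holds as a low-priority improvement. For this omission alone, the estimate is unbiased and the test is nominal or slightly conservative. That should not be read as a statement about the planned test as a whole. It says nothing, for example, about the fallback single imputation of Week 52 height in 14.3.2.

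With an even split, 4 to 22 subjects and residual SD 2.80, the loss is 0.1 to 0.4 power points at a gap of 1.0 cm/yr and 0.7 to 3.2 points at an extreme 2.8 cm/yr. If 2.80 is the total SD, only power above the planned 90% is forgone. These are illustrations, not limits, because group size, split and residual gap are all assumed. If the gap is zero, there is nothing to gain.

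**What to change.** Before unblinding, add one binary term (separate randomisation scheme, yes or no) to the ANCOVA models in 14.3.2, 14.4.1 and 14.4.2. Carry it into the analyses that reuse those models: the per-protocol repeats, the washout sensitivity analysis, the completer analysis, and the analysis excluding assessments after limb lengthening or hormone treatment. Do not make inclusion depend on a head count, so that the model stays fully pre-specified. State that the term is left out of the subgroup models in 14.7. State also whether it enters the PROC MI variable list, since the imputation may rest on as few as five reference subjects. The baseline-AGV fallback imputation needs no change.

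The cost is one degree of freedom and an amendment to a final SAP. If the group is not prognostic, about 0.01 power points are lost with an even split and up to about 0.28 with a 3 v 1 split. In a very small, unevenly split group the term gives no net gain at moderate gaps.
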